**Table 10-2: Phase 1 liver chemistry stopping criteria and follow-up assessments**

Liver Chemistry Stopping Criteria – Liver Stopping Event	
ALT-absolute	
ALT <math>\geq 3 \times</math>ULN
 
If ALT <math>\geq 3 \times</math>ULN AND bilirubin <math>\geq 2 \times</math>ULN (>35% direct bilirubin) OR INR >1.5, report as an SAEa,b
 
See additional actions and follow-up assessments listed below

Required Actions and Follow-up Assessments	
Actions	Follow-Up Assessments

 
• Immediately discontinue study intervention
 
• Report the event to UCB within 24 hours
 
• Complete the liver event eCRF, and complete an SAE data collection tool if the event also met the criteria for an SAEb
 
• Perform liver function follow-up assessments
 
• Monitor the participant until liver function test abnormalities resolve, stabilize, or return to baseline (see MONITORING)
 
• Consider the need for a toxicology screening.
 
 
MONITORING:
 
If ALT <math>\geq 3 \times</math>ULN AND bilirubin <math>\geq 2 \times</math>ULN or INR >1.5
 
 
• Repeat liver function tests (include ALT, AST, alkaline phosphatase, bilirubin) and perform liver function follow-up assessments within 24 hours.
 
• Monitor participant twice weekly until liver function test abnormalities resolve, stabilize, or return to baseline.
 
• A specialist or hepatology consultation is recommended.
 
 
If ALT <math>\geq 3 \times</math>ULN AND bilirubin <2xULN and INR <math>\leq 1.5</math>:
 
 
• Repeat liver function tests (include ALT, AST, alkaline phosphatase, bilirubin) and perform liver function follow-up assessments within 24 to 72 hours
 
• Monitor participants weekly until liver function abnormalities resolve, stabilize, or return to baseline
 
	
 
• Viral hepatitis serologyc
 
• Obtain INR and recheck with each liver chemistry assessment until the transaminases values show downward trend
 
• Obtain blood sample for pharmacokinetic (PK) analysis within 2 days after the most recent dosed
 
• Serum creatine phosphokinase and lactate dehydrogenase
 
• Fractionate bilirubin, if total bilirubin <math>\geq 2 \times</math>ULN
 
• Complete blood count with differential to assess eosinophilia
 
• Record the appearance or worsening of clinical symptoms of liver injury (eg, fatigue, nausea, vomiting, right upper quadrant pain), or hypersensitivity, on the AE eCRF
 
• Record use of concomitant medications (including acetaminophen, herbal remedies, and other over-the-counter medications) on the concomitant medications eCRF
 
• Record alcohol use on the liver event alcohol intake eCRF
 
 
If ALT <math>\geq 3 \times</math>ULN AND bilirubin <math>\geq 2 \times</math>ULN or INR >1.5:
 
 
• Anti-nuclear antibody, anti-smooth muscle antibody, Type 1 anti-liver kidney microsomal antibodies, and quantitative total IgG or gamma globulins
 
• Serum acetaminophen adduct high performance liquid chromatography assay (quantifies potential acetaminophen contribution to liver injury in participants with
 

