5.6.3.1.3 Potential Drug-Induced Liver Injury

Data from subjects with any of the laboratory results meeting the criteria for potential drug-induced liver injury (PDILI) (below) will be summarized by treatment group and visit.

PDILI Criteria:

- Alanine aminotransferase (ALT) or Aspartate aminotransferase (AST) $\geq 5x$ Upper limit of normal (ULN)
- ALT or AST increase $\geq 3x$ ULN and Total bilirubin $\geq 2x$ ULN
- (ALT or AST increase $\geq 3x$ ULN) and Total bilirubin $\geq 2x$ ULN and ALP $< 2x$ ULN
- (ALT or AST $\geq 3x$ ULN) and (eCRF question for “Is the subject exhibiting we symptoms of hypersensitivity” = Yes or eCRF question for “Is the subject exhibiting symptoms of. Hepatitis” = Yes at the same date +/-2 days).
- (ALT or AST) $\geq 3x$ ULN (and $\geq 2x$ Baseline) and $< 5x$ ULN and Total bilirubin $< 2x$ ULN and (eCRF question for “Is the subject exhibiting symptoms of hypersensitivity” = No and eCRF question for “Is the subject exhibiting symptoms of Hepatitis” = No at the same date +/-2 days)
- (ALT or AST) $\geq 5x$ ULN (and $\geq 2x$ Baseline) and Total bilirubin $< 2x$ ULN (eCRF question for “Is the subject exhibiting symptoms of hypersensitivity” = No and eCRF question for “Is the subject exhibiting symptoms of Hepatitis” = No at the same date +/-2 days)

A listing will also be created only visits for which at least one of the above criteria was fulfilled for a given participant and will display all results obtained at that visit for the specified parameters.

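### An isolated ALT or AST of 3 to <5×ULN drops out of the SAP's liver-injury rows and listing when the symptom answers are missing, partial or dated more than 2 days away

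*Protocol*

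**What the plan says.** SAP 5.6.3.1.3 lists six PDILI criteria, numbered here in the order printed. The first is "Alanine aminotransferase (ALT) or Aspartate aminotransferase (AST) $\geq 5x$ Upper limit of normal (ULN"), with no condition on bilirubin or symptoms. The second and third require bilirubin of at least 2×ULN. The fourth takes ALT or AST ≥3×ULN with a positive answer to an eCRF question on hypersensitivity or on hepatitis symptoms, "Yes at the same date +/-2 days". The fifth covers 3 to <5×ULN with bilirubin below 2×ULN and a value at least twice Baseline, and needs No to both questions in the same window. The sixth is the counterpart of the fifth from 5×ULN upward. On the listing, the SAP says: "A listing will also be created only visits for which at least one of the above criteria was fulfilled".

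Protocol Appendix 6, Table 10-2, acts on ALT ≥3×ULN. When bilirubin is below 2×ULN and INR is at most 1.5, the site is to repeat the liver tests and "perform liver function follow-up assessments within 24 to 72 hours". Among the follow-up items is "Record the appearance or worsening of clinical symptoms of liver injury" or of hypersensitivity, and the place named for this is the AE eCRF.

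SAP 6.1.9.1.2 sets the marked-abnormality threshold for ALT and for AST above 5×ULN.

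**The concern.** A liver-safety table should show every transaminase rise that reaches its lowest threshold. Here, between 3 and 5×ULN with normal or near-normal bilirubin, inclusion depends on whether two form questions were answered, how they were answered, and on what date. An unanswered question does not lead to a row for unknown symptom status. It removes the visit from the table and from the listing that goes with it.

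Safety is the primary objective, and each cohort has 6 active and 2 placebo participants. Few such rises can be expected, so one omitted visit could change a liver-injury row from one participant to none. A reader of that table could not tell this apart from no event.

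**Working it through.** **Inputs.** The six criteria and the listing rule come from SAP 5.6.3.1.3. The trigger, the follow-up window and the symptom instruction come from Protocol Table 10-2. The marked-abnormality threshold comes from SAP 6.1.9.1.2. The visit days come from Protocol Table 1-1. The plan gives no figure to reproduce.

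**Step 1: which criteria can an isolated 3 to <5×ULN value meet?**

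| Criterion | Needs | Reachable? |
|---|---|---|
| 1 | ≥5×ULN | No |
| 2 | bilirubin ≥2×ULN | No |
| 3 | bilirubin ≥2×ULN and ALP <2×ULN | No |
| 4 | at least one Yes within ±2 days | Yes, if answered so |
| 5 | both No within ±2 days, and ≥2×Baseline | Yes, if answered so |
| 6 | ≥5×ULN | No |

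**Step 2: answer patterns.** Take 4×ULN with bilirubin 1×ULN. Each question can be Yes, No or missing, which gives 3 × 3 = 9 patterns. They are not equally likely; the count only shows which ones fail.

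- Answers within 2 days, Baseline 1.0×ULN: at least one Yes occurs in 9 − (2 × 2) = 5 patterns (criterion 4). Both No is 1 pattern (criterion 5). The remaining 9 − 5 − 1 = 3 meet nothing: both missing, or one No with the other missing (two ways).
- Answers within 2 days, Baseline 2.2×ULN: 2 × 2.2 = 4.4 > 4, so the both-No pattern fails too, and 3 + 1 = 4 of 9 meet nothing. This is a boundary case. Exclusion criterion 12 bars ALT or AST above 1.0×ULN (one repeat is allowed for small excesses), and for any Baseline up to 1.5×ULN a value of 3×ULN already satisfies the ≥2×Baseline condition.
- Answers 3 days away: 9 of 9 meet nothing.
- Contrast: 6×ULN with no answers still meets criterion 1. The gap is confined to 3 to <5×ULN.

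**Step 3: timing.** 72 h / 24 = 3 days, which is outside ±2 days.

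- If ±2 days means 48 hours, the share of the 24 to 72 hour window that falls outside is (72 − 48) / (72 − 24) = 24/48 = 50%.
- If it means calendar dates, a sample drawn t hours after midnight leaves t/48 outside: 8/48 = 17% at 08:00 and 12/48 = 25% at 12:00, with a range of 0% to 50%.

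These are shares of the permitted window, not probabilities of loss. The visit schedule has a similar interval: chemistry is drawn on Day 10 and the next scheduled visit is Day 13, 3 days later.

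**Step 4: where the value still shows.**

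| Output | Shows the value? | Identifies potential liver injury? |
|---|---|---|
| PDILI rows and PDILI listing | Not if answers are missing, partial or late | Yes |
| Marked-abnormality flag (>5×ULN) | No | No |
| Abnormal and out-of-range listings (SAP 5.6.3.1) | Yes, with reference range | No |
| Shift tables (SAP 5.6.3.1.2) | As normal to high only, so 1.1×ULN and 4×ULN look the same | No |
| Descriptive statistics (SAP 5.1, 5.6.3.1.1) | A group maximum could show it | No |

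**Step 5: analyte.** Table 10-2 names ALT as its trigger. SAP 5.6.3.1.3 counts ALT or AST, as does the potential Hy's Law definition in Protocol 8.3.6. On Table 10-2 alone, an AST-only rise does not set off the follow-up that might prompt the symptom answers.

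**The case against.** The strongest case on the other side has four parts.

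**The value is not hidden.** A reader might infer from the PDILI rules that such a case appears in no output at all. The documents do not support that. SAP 5.6.3.1 lists abnormal values together with all of that participant's values for the parameter, and the shift tables and maxima also carry it. Symptoms entered on the AE eCRF reach the TEAE tables. Protocol 8.2.4 sends clinically relevant laboratory changes to the AE section, and the SAP has a hepatic AE-of-focus table. All of this stands. What remains is that none of the laboratory outputs labels the value as potential liver injury.

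**The timing conflict is not proven.** A reader might infer that a site following Table 10-2 on Day +3 necessarily misses the SAP window. No text ties the two Yes/No questions to the 24 to 72 hour follow-up. Table 10-2 also orders the site to "Complete the liver event eCRF, and complete an SAE data collection tool if the event also met the criteria for an SAE", with no deadline for the liver form of its own. The SAP relies on an eCRF version that is not among the documents. This objection stands, so the 72-hour link is an inference. The dependence on answers inside ±2 days does not rest on it.

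**Repeat testing narrows the gap.** The same Table 10-2 item orders repeat ALT and AST. If the repeat is still ≥3×ULN and the questions are answered that day, the repeat visit meets a row when at least one answer is Yes, or when both are No and the Baseline condition holds. The exposed cases are mainly values that have fallen below 3×ULN by the repeat, and visits with missing or partial answers.

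**An AST-only case is not certain to be lost.** Criteria 4 and 5 accept AST when the questions are answered. Protocol 8.2.4 has clinically significant results repeated, and Appendix 6 requires potential liver injury to be assessed. Figure 7-1 is not shown and its legend defines AST, so the ALT-only reading rests on Table 10-2.

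**Conclusion.** The point holds for the liver-injury outputs. An isolated ALT or AST of 3 to <5×ULN is counted there only through suitable symptom answers dated within ±2 days. Without them the visit is absent from every PDILI row and from the PDILI listing, and it carries no marked-abnormality flag. This follows from the SAP's wording alone. It rests on reading the criteria as printed, with a missing answer counted as neither Yes nor No, consistent with the SAP's general rule that missing data are not imputed.

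The causes suggested by Table 10-2 (follow-up at up to 72 hours, symptoms sent to the AE eCRF, an ALT trigger) make missing or late answers possible. They do not show that such answers will occur.

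No frequency of lost cases can be derived. The documents give no transaminase incidence. An assumed one would yield the chance of any ≥3×ULN value among 32 participants, which includes cases the table captures unconditionally. The loss would be at most a few visits in a descriptive table. The primary endpoint, incidence of TEAEs, is defined separately. This is an inexpensive improvement to liver-safety reporting and does not undermine the analysis.

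**What to change.** In SAP 5.6.3.1.3, add a row for ALT or AST ≥3×ULN that carries no other condition, split into 3 to <5×ULN and ≥5×ULN. Show symptom status beneath it as Yes / No / not recorded. Use the same condition as a trigger for the PDILI listing. The existing six criteria can stay. With this row, inclusion no longer depends on when or where the two questions are completed.

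The sponsor should also reconcile Table 10-2 with SAP 5.6.3.1.3 on two points: the analyte (ALT against ALT or AST) and the timing (up to 72 hours against ±2 days). The SAP should state which eCRF page holds the two questions and which date on it is used for matching. Which clinical trigger or follow-up interval applies is for the sponsor to settle and is not proposed here.

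The cost is a SAP wording change and a small amount of programming for the row, the symptom breakdown and the listing trigger. No new data are needed. Reconciling Table 10-2 may need a protocol clarification, but the added row does not have to wait for it.

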
**Table 10-2: Phase 1 liver chemistry stopping criteria and follow-up assessments**

Liver Chemistry Stopping Criteria – Liver Stopping Event	
ALT-absolute	ALT $\geq 3 \times$ ULN If ALT $\geq 3 \times$ ULN AND bilirubin $\geq 2 \times$ ULN (>35% direct bilirubin) OR INR >1.5, report as an SAE a,b See additional actions and follow-up assessments listed below
Required Actions and Follow-up Assessments	
Actions	Follow-Up Assessments
	definite or likely acetaminophen use in the preceding week [James et al, 2009]) NOTE: Not required in China. 
 
Liver imaging (ultrasound, magnetic resonance, or computerized tomography) and/or liver biopsy to evaluate liver disease; complete liver imaging and/or liver biopsy eCRFs
 

AE=adverse event; ALT=alanine aminotransferase; AST=aspartate aminotransferase; eCRF=electronic case report form; HBsAg=hepatitis B surface antigen; HBcAb=hepatitis B core antibody; IgG=immunoglobulin G; IgM=immunoglobulin M; INR=International Normalized Ratio; PK=pharmacokinetic; RNA=ribonucleic acid; SAE=serious adverse event; ULN=upper limit of normal

- a Serum bilirubin fractionation should be performed if testing is available. If serum bilirubin fractionation is not immediately available, discontinue study intervention if ALT  $\geq 3 \times$ ULN. Additionally, if serum bilirubin fractionation testing is unavailable, record the absence/presence of detectable urinary bilirubin on dipstick which is indicative of direct bilirubin elevations suggesting liver injury.
- b All events of ALT  $\geq 3 \times$ ULN and bilirubin  $\geq 2 \times$ ULN (>35% direct bilirubin) or ALT  $\geq 3 \times$ ULN and INR >1.5 may indicate severe liver injury (possible ‘Hy’s Law’) and must be reported as an SAE (excluding studies of hepatic impairment or cirrhosis). The INR measurement is not required and the stated threshold value will not apply to participants receiving anticoagulants.
- c Hepatitis A IgM antibody; HBsAg and HBcAb; hepatitis C RNA; cytomegalovirus IgM antibody; Epstein-Barr viral capsid antigen IgM antibody (or if unavailable, heterophile antibody or monospot testing); and hepatitis E IgM antibody.
- d PK sample may not be required for participants known to be receiving placebo or non-comparator interventions. Record the date/time of the PK blood sample draw and the date/time of the last dose of study intervention prior to the PK blood sample draw on the CRF. If the date or time of the last dose is unclear, provide the participant’s best approximation. If the date/time of the last dose cannot be approximated OR a PK sample cannot be collected in the time period indicated above, do not obtain a PK sample. Instructions for sample handling and shipping are in the Study Reference Manual.

---

**10.7 Appendix 7: Medical device AEs, ADEs, SAEs, and device deficiencies: definition and procedures for recording, evaluating, follow-up, and reporting**

Not applicable

**PUBLIC COPY**  
This document cannot be used to support any marketing authorization application and any extensions or variations thereof.

## 10.8 Appendix 8: Rapid alert procedures

The aim of the Rapid Alert process is to stop the exposure to the study medication or concerned study procedure as soon as possible, following a confirmed or suspected safety issue, preventing its reoccurrence in other study participants. Upon occurrence of an SAE and/or another safety event including stopping rules for all cohorts which may constitute a study hold criteria, irrespective of its relationship with the study medication or the study conduct, the **investigator must notify the study sponsor as soon as possible** (ideally within 2 hours of becoming aware of the event) by the following process:

1. A phone call to the Study Physician to alert them a safety event has been identified.
2. If the investigator is not able to reach the Study Physician, they should call the 24h rapid response helpline number. Upon receipt of a call from an investigator, the 24/7 helpline will contact a physician from UCB who will return the call to the investigator.
3. Additionally, send a completed “Investigator (S)AE Report Form for Development Drug (For Rapid Alert Studies)” to the fax/email for Rapid Alert provided at the front of the protocol. The form should include assessed seriousness, severity, and causality and should be filed in the Study Investigator’s File.

Both the phone call and the completed form from the investigator are crucial in assessing the safety of the study medication and in determining whether the event requires immediate action to place the study on hold and/or expedite reporting to the regulatory authorities. The (S)AE form should be completed in English and provided even if the data are incomplete, or if it is obvious that more data will be needed in order to draw any conclusions about the diagnosis or causality. Additional information (eg, laboratory reports) received by the investigator must be provided within 24 hours. All documents in the local language must be accompanied by a translation in English, or the relevant information included in the same document must be summarized in English in the (S)AE form.

During the call between the investigator and the UCB physician the safety issue will be discussed to determine if there is sufficient evidence to declare a protocol hold criteria has been met. If the investigator and UCB physician agree a stopping a criterion has not been met, dosing of the study may continue as per the study protocol and the discussion between the investigator and the UCB physician should be documented. UCB will not downgrade the investigator decision to halt the study if the investigator considered that a stopping criterion has been fulfilled.

In all other circumstances, the investigator will be instructed to suspend dosing and the UCB physician will arrange an urgent, internal UCB Rapid Alert Team meeting. The Rapid Alert Team will review the information provided at the call along with the (S)AE form to determine whether or not a protocol hold criterion has been met. If it is determined the criterion has not been met, UCB will contact the investigator and inform them to recommence dosing. If it is determined a hold criterion has been met, UCB will contact all investigators and notify them of the formal hold.

If the investigator believes a protocol stopping criterion has been met, and they are unable to contact UCB prior to the next dose being due, they should postpone any further dosing until they

---

have obtained feedback from UCB. In these circumstances dosing may be restarted if UCB and the investigator subsequently agree that no stopping criteria have been met.

PUBLIC COPY  
This document cannot be used to support any marketing authorization application and any extensions or variations thereof.

---

**10.9 Appendix 9: Country specific requirements**

Not applicable

PUBLIC COPY  
This document cannot be used to support any marketing authorization application and any extensions or variations thereof.

## 10.10 Appendix 10: Abbreviations and trademarks

ADA	anti-drug antibody
ADE	adverse device effect
ADL	activities of daily living
AE	adverse event
ALP	alkaline phosphatase
ALT	alanine aminotransferase
AST	aspartate aminotransferase
AUC (0-t)	area under the concentration-time curve from 0 to time t;
AUC(IgG)	area under the Total IgG-time curve
BP	blood pressure
CSF	cerebrospinal fluid
C max	maximum plasma concentration
COVID-19	coronavirus disease-19
CRO	contract research organization
CT	computed tomography
ECG	electrocardiogram
eCRF	electronic Case Report form
FcRn	neonatal Fc receptor
GCP	Good Clinical Practice
HDL	high-density lipoprotein
HRT	hormonal replacement therapy
IB	Investigator's Brochure
ICH	International Council for Harmonisation
IEC	Independent Ethics Committee
ICF	informed consent form
IgG	immunoglobulin G
IMP	investigational medicinal product
ISRQ	injection site reaction questionnaire
ITP	immune thrombocytopenia
LDL	low-density lipoprotein
LLOQ	lower limit of quantification

---

MG	myasthenia gravis
MP	manual push
PD	pharmacodynamic(s)
PK	pharmacokinetic(s)
QTc	corrected QT
QTcF	QT interval corrected for heart rate using Fridericia's formula
SAE	serious adverse event
SAP	Statistical Analysis Plan
SARS-CoV-2	severe acute respiratory syndrome coronavirus 2
SC	subcutaneous(ly)
SMC	Safety Monitoring Committee
SIAQ	self-injection assessment questionnaire
TB	tuberculosis
TEAE	treatment-emergent adverse event
$t_{\min}$	time to minimum IgG-level
ULN	upper limit of normal
WOCBP	woman of childbearing potential

## 10.11 Appendix 11: Protocol amendment history

The Protocol Amendment Summary of Changes Table for the current amendment is located directly before the Table of Contents.

### Amendment 1 (16 Mar 2021)

#### Overall Rationale for the Amendment

The primary reason for this protocol amendment is to incorporate the changes requested by the Medicines & Healthcare products Regulatory Agency to the original protocol.

Section # and Name	Description of Change	Brief Rationale
1.1 Synopsis, Overall design 4.1 Overall design	The text “with application of the Cohort 1 stopping rule (see Section 6.7)” has been deleted.	Dosing must be halted if any of the stopping criteria are observed in any of the study cohorts and not only if observed in Cohort 1.
1.3 Schedule of activities	Table 1.1: Schedule of activities: The row for “Medical history” has been deleted.	The medical history assessment is captured in the “Medical/procedure history” assessment, and therefore this was a duplicated assessment.
2.3 Benefit/risk assessment	The text has been updated to reflect that the stopping rules are applicable to all cohorts.	Dosing must be halted if any of the stopping criteria are observed in any of the study cohorts and not only if observed in Cohort 1.
5.1 Inclusion criteria	Inclusion criterion #8: This criterion has been updated to clarify that woman of childbearing potential must follow contraceptive guidance for at least 90 days after the final dose of investigational medicinal product (IMP).	To ensure the duration of contraception after the last dose of IMP in case of early termination.
5.4 Screen failures	Updated to clarify that repeat laboratory screening tests are not restricted to those that were out-of-range. In addition, a time frame for the repeat assessments has been added.	To clarify that the repeat (visit) should be planned within the time frame of 28 days between the initial screening day and Day 1 prior to dosing.
6.3.1.2 Breaking the treatment blind in an emergency situation	Clarified that the unblinding procedure in case of an emergency is performed by the investigator.	The responsibility to break the treatment code in emergency situations resides solely with the investigator.

Section # and Name	Description of Change	Brief Rationale
6.7.1 Stopping rules for all cohorts	The title and text have been updated to reflect that the stopping rules are applicable to all cohorts. In addition, it has been clarified that further dosing is suspended if any of the stopping criteria are met.	Dosing must be halted if any of the stopping criteria are observed in any of the study cohorts and not only if observed in Cohort 1.
10.1.5 Committees structure	Updated to include the following sentence: “The principal investigator will participate in the decision of continuing dosing of the remaining participants on each of these cohorts based on the safety data obtained from the sentinel participants dosing.”	The UCB Safety Monitoring Committee (SMC) core members includes not only UCB members but also the principal investigator
10.8 Appendix 8: Rapid alert procedures	Updated to clarify the sponsor will not downgrade the investigator decision to halt the study if the investigator considered that a stopping criterion has been fulfilled.  In addition, it has been clarified that the stopping rules are applicable to all cohorts.	The investigator is responsible for all study-related medical decisions.  Dosing must be halted if any of the stopping criteria are observed in any of the study cohorts and not only if observed in Cohort 1.

